6.1.4.1 Placebo for Elotuzumab

The placebo for elotuzumab will be 0.9% sterile normal saline for injection. Placebo for elotuzumab will be prepared at each site's investigational pharmacy. Investigational pharmacies will use sterile normal saline that is produced by an FDA registered facility as designated by the presence of a National Drug Code (NDC) number on product labeling. Product information including manufacturer, lot number, and expiration date will be documented on participant-specific accountability log during each preparation and dispensing. Placebo for elotuzumab will be given as intravenous infusion bag, volume matched to elotuzumab. More detailed information will be included in the pharmacy manual.

6.1.4.2 Elotuzumab Administration and Monitoring**6.1.4.2.1 Pre-medication**

Pre-medicate approximately 45-90 minutes prior to each elotuzumab/placebo infusion with the following:

- Methylprednisolone 50 mg intravenously
- Diphenhydramine 25-50 mg orally or intravenously
- Acetaminophen 650 mg orally
- H2 blocker: famotidine (20 mg intravenously or orally) or equivalent H2 blocker

6.1.4.2.2 Administration

The infusion is to be administered through a sterile, nonpyrogenic, low protein binding in-line filter (with a pore size of 0.2 μ m to 1.2 μ m) using an automated infusion pump. Initiate infusion at a rate of 0.5 mL per minute. The infusion may be increased in a stepwise fashion as described in the table below if no infusion reaction. The maximum rate should not exceed 5 mL per minute.

First Dose		Second Dose		Subsequent Doses
Time Interval	Rate	Time Interval	Rate	Rate
0-30 min	0.5 mL/min	0-30 min	3 mL/min	5 mL/min
30-60 min	1 mL/min	\geq 30 min	4 mL/min	
\geq 60 min	2 mL/min	---	---	

Elotuzumab must not be administered as an IV push or bolus. Do not mix elotuzumab, or administer as an infusion, with any other medicinal products.

In Part 1A, there must be a minimum of four full days between each weekly infusion. In Part 1B and 2, there must be a minimum of seven full days between each infusion.

If an infusion is missed for reasons other than those requiring premature discontinuation (Section 6.6), a single intermediate delayed infusion may be permitted if it can be administered with the minimum windows before the next scheduled infusion that are noted above. Additional details on toxicity management and criteria for the resolution of specific adverse events before restarting infusions are given in Section 6.4.

In Part 1A, if the infusion schedule has been interrupted, administration of infusions may be adjusted to permit administration of 4 doses prior to the week 11 visit. In Part 1B and 2, no infusions can be administered after Week 44 in order to evaluate the durability of a disease response or complete remission at Week 48.

6.1.4.2.3 Monitoring

Elotuzumab/placebo infusions will occur in a setting with access to advanced cardiovascular life support (ACLS) certified personnel, resuscitative drugs, monitoring devices, and CPR equipment. Vital signs must be assessed prior to the infusion, approximately every 15 minutes during the infusion, at the end of the infusion, and 1 hour after completion of the infusion or per comparable institutional standards.

If an infusion reaction occurs, the infusion should be interrupted and medical management instituted as needed (e.g., glucocorticoids, epinephrine, bronchodilators, or oxygen). See protocol Section 6.4.1 for additional guidelines on managing an infusion reaction.

6.2 Drug Accountability

Under Title 21 of the Code of Federal Regulations (21CFR §312.62) the investigator will maintain adequate records of the disposition of the investigational agent, including the date and quantity of the drug received, to whom the drug was dispensed (participant-by-participant accounting), and a detailed accounting of any drug accidentally or deliberately destroyed. The investigator will ensure that the investigational product is stored as specified in the protocol and pharmacy manual in a secured area within the pharmacy, with access limited to authorized study personnel. For this study, these responsibilities are delegated to each site's Pharmacist of Record (PoR).

Records for receipt, storage, use, and disposition will be maintained by the study site. A drug-dispensing log will be kept current for each participant. This log will contain the identification of each participant and the date and quantity of drug dispensed. All remaining unused investigational product will be returned to the sponsor or sponsor's representative after study termination.

All records regarding the disposition of the investigational product will be available for inspection.

6.3 Assessment of Participant Dosing Compliance

Elotuzumab/placebo will be administered intravenously at sites by trained medical staff. Compliance, therefore, will be monitored by the site and documented on the electronic Case Report Form (eCRF).

Dosing compliance with oral prednisone (see Protocol Section 7.1.1.3) will be assessed by pill count at each visit. Study personnel will calculate compliance in the presence of the participant so that reinforcement/re-education can be conducted as needed. Drug accountability and compliance will be documented on the source visit record and in the electronic data capture system.

6.4 Toxicity Prevention and Management

6.4.1 Infusion Reactions

Infusion reactions in the pivotal studies in multiple myeloma are described in Protocol Section 5.1.1. Pre-medications are described in Protocol Section 6.1.4.2.1. In the event of a Grade 2 infusion reaction, suspend the infusion and institute appropriate medical and supportive measures per institutional standards. Upon complete or partial resolution (Grade 1), restart elotuzumab/placebo at 0.5 mL/min. Gradually increase infusion rate by 0.5 mL/min every 30 minutes as tolerated to the rate at which the reaction occurred. Resume rate escalation regimen (Protocol Section 6.1.4.2.2) if there is no recurrence of infusion reaction.

In the event of an infusion reaction, monitor vital signs at least every 30 minutes for 2 hours after completion of the infusion and otherwise as clinically indicated. If the infusion reaction recurs, stop the infusion and do not restart on that day. A Grade 3 or higher infusion reaction including anaphylaxis will require permanent discontinuation of elotuzumab/placebo. If anaphylaxis occurs, immediately and permanently discontinue elotuzumab/placebo and administer emergency medical therapy.

6.4.2 Infection

Elotuzumab should not be given during periods of active infection. Signs and symptoms of infection that warrant investigator consideration to withhold study drug administration include but are not limited to the following:

- Fever > 38° C
- Symptoms of upper/lower respiratory or urinary tract infection
- Vomiting/diarrhea within 24 hours

Discontinue study drug permanently in the event of a Grade 4 infection.

Guidance for proceeding with study drug administration following a Grade 3 infection and resolution includes:

- Allowing at least one month between restarting the study drug and start of the infection
- Full recovery of acute symptoms and effects
- Completion of treatments for the infection
- Clinical determination that participant is deemed fit to resume elotuzumab

Guidance for proceeding with study drug administration following a ≤ Grade 2 infection and resolution includes:

- Improvement/resolution of symptoms
- Resolution of fever for at least 24 hours
- Antibiotic administration for a minimum of 48 hours (as applicable)
- Initial cultures negative at 48 hours (if obtained) unless appropriate antibiotic therapy instituted 48 hours in advance of the infusion

Elotuzumab should not be given if a participant has a positive SARS-CoV-2 (COVID-19) viral test. If a participant develops a SARS-CoV-2 (COVID-19) infection, elotuzumab may be resumed one month after start of the infection, once the participant has recovered from the infection's acute symptoms and effects, stopped treatments for the infection, including supplemental oxygen, and is deemed fit to resume elotuzumab. Instructions for resuming the protocol-specified prednisone taper are detailed in section 7.1.1.3.

Once the infection resolves, elotuzumab/placebo may be restarted at the next scheduled dose. If the infection resolves in time for a delayed infusion to be administered in the minimum window before the next scheduled infusion specified in Section 6.1.4.2.2, a single intermediate administration is permitted. In Part 1A, if the infusion

schedule has been interrupted, administration of infusions may be adjusted to permit administration of 4 doses prior to the week 11 visit. In Part 1B and 2, no infusions can be administered after Week 40 in order to evaluate the durability of a disease response or complete remission at Week 48.

6.4.2.1 Varicella Zoster Infection and Reduced Response to Vaccination

Participants will be informed about the potential for Varicella zoster (herpes zoster) infections. Following a discussion with the investigator as part of the consent process, participants who have not received the recombinant zoster vaccination (Shingrix®) may elect to receive the first dose of the vaccine prior to participating in the study as part of standard of care. In this situation, the second vaccine dose may be administered as recommended 4-6 months later, as standard of care and not part of the study. Participants will be counseled about the potential effects of elotuzumab on responses to immunization and the need to follow up on the status of their immunity with their primary care providers following participation in the trial.

6.4.2.2 General Principles for Protection from COVID-19

The following principles guide the conduct of the trial during the COVID-19 public health emergency:

- The safety of participants is paramount. Any decisions to begin, continue, or stop enrollment in the study will be made with consideration of the potential impact of COVID-19 on the safety of the participants. Trial participants will be kept informed of any changes in the study and any impacts on their participation. The nature of the study intervention, a targeted therapy with immunosuppressive properties, requires careful monitoring of the study participants and the status of the rates of COVID-19 infections at the individual clinical sites.
- The decision to continue or discontinue the experimental intervention will be made with the safety and welfare of the trial participant in mind. This decision will be made jointly between the sponsor, study chair, site investigator, and Institutional Review Board. Due consideration will be given to the fact that elotuzumab/corticosteroids may interfere with the ability of the participant's immune system to produce neutralizing antibodies against SARS-CoV-2 and could significantly increase the susceptibility to and severity of infection.
- Participants should be advised to increase their protection from COVID-19 infection by doing the following: wearing a well-fitting mask indoors in public in areas or when around others who are not up to date on their COVID-19 vaccines or not eligible to receive COVID-19 vaccines, stay 6 feet away from others, avoid poorly ventilated spaces and crowds, and wash hands often. These recommendations are subject to change, but are updated at:
<https://www.cdc.gov/coronavirus/2019-ncov/prevent-getting-sick/prevention.html>
- In certain cases, the participant may not be able to come to the study site, or local institutional policies or other factors may intervene to limit access to the research site. The sponsor in consultation with site personnel will determine if alternative methods for assessments are necessary and feasible, and will assure the safety of the study participant. For example, in-person visits may be substituted with virtual visits or phone contact, or trial participants may come to an alternative site for completion of their safety assessments (e.g. off-campus laboratory). Changes in modality/timing of study visits, data collection, and/or other protocol deviations will be documented accordingly.

- Urgent or emergent changes in the protocol as a result of COVID-19 infection or the rising rates of COVID infections to protect the safety of participants may be implemented immediately without IRB approval, with concurrent notification of the IRB. The sponsor and the investigators will work closely with IRB to implement any required changes in the protocol or the consent form, as appropriate and submit any revised documents to FDA per current guidance.
- Participants should continue to receive SARS-CoV-2 vaccinations per CDC and FDA recommendations during the course of the study.
- Any participant who has close contact with a SARS-CoV-2 infected individual should be evaluated for post-exposure prophylaxis as soon as possible after exposure.

6.4.2.3 SARS-CoV-2 Prevention

The AIG01 protocol requires specific measures in the interest of preventing SARS-CoV-2 infections. The current and future FDA approval and emergency use authorization of SARS-CoV-2 vaccines and updates to CDC recommendations on vaccinations programs to promote public health may impact the enrollment and monitoring of trial participants. The sponsor in consultation with the investigators will determine if any protocol modifications are necessary as the situation evolves. Vaccine immune response may be blunted by treatment with corticosteroids and elotuzumab.

Specific measures designed to prevent SARS-CoV-2 infections include:

- Participants must be confirmed negative for SARS-CoV-2 by antigen test within 24 hours of each infusion. Participants will be provided antigen tests by the site, test themselves, and provide proof of negativity.

6.4.3 Hepatotoxicity

IgG4-RD seldom affects hepatocytes directly. Abnormalities of the liver noted in IgG4-RD are usually the result of biliary tract disease. We do not anticipate, therefore, an increased propensity to liver injury among the IgG4-RD participants in this trial. Nevertheless, the eligibility criteria have been written conservatively to exclude participants with significant risk-factors for hepatic insult. Liver function tests will be monitored frequently prior to infusions with elotuzumab/placebo and throughout the follow-up period to assess for potential drug-induced liver injury, with particular concern for hepatic transaminase elevation and hyperbilirubinemia. The specific laboratory measures of concern, which correspond to Grade 3 adverse events, are:

- ALT or AST elevation > 5 times ULN,
- Total bilirubin > 3 times ULN. If Gilbert's disease, total bilirubin > 3 times baseline value.

A grade 3 or higher elevation in liver enzymes, defined as ALT or AST > 5 times ULN or a total bilirubin > 3 times the upper limit of normal, that persists longer than 5 days will result in discontinuation of elotuzumab/placebo. For a grade 3 or higher event that resolves in less than 5 days, elotuzumab/placebo may be restarted under the schedule noted in Section 6.4.2.

6.4.4 Primary Malignancy

The eligibility criteria have been written conservatively to exclude individuals with a history of malignancy within 5 years (except for successfully treated in situ cervical cancer, resected squamous cell or basal cell carcinoma of the skin). Given the information on second primary malignancies in the elotuzumab prescribing information, attention will be paid to monitoring for malignancy as consistent with standard of care.

Participants over the age of 50 should have age-appropriate cancer screenings at the investigator's discretion prior to enrollment and throughout the course of the study. For additional information, consult the American Cancer Society (ACS) reference below: <http://www.cancer.org/healthy/toolsandcalculators/reminders/screening-recommendationsby-age>

6.5 Submandibular Gland Biopsy

During Part 1A, an optional submandibular gland biopsy (MGH participants only) will be performed between screening and Baseline/Day 0 and between Weeks 16 and 24 to evaluate the tissue response to study therapy. During Part 1B and 2, an optional submandibular gland biopsy will be performed prior to the Baseline/Day 0 Visit, following eligibility confirmation, and between Weeks 40 and 44. The participants will be instructed to suspend aspirin or NSAID intake 3-7 days before the procedure. Core needle biopsy of the submandibular gland is generally only slightly painful and rarely associated with significant morbidity. However, it is possible that a biopsy site might become infected, requiring antibiotic treatment or surgical debridement. The biopsy is done through normal appearing overlying skin. After application of a topical anesthetic, local anesthetic with vasoconstrictor is infiltrated into the area around the submandibular gland. An ice pack is then placed on the skin in the area of the biopsy to reduce swelling and bruising (risk management). Part of the submandibular gland biopsy will be placed in normal saline for special studies. Part will be placed in a neutral buffered formalin for studies using paraffin-embedded sections. The remaining gland will be placed on an aluminum foil boat and then transferred into a Nunc vial, which is capped and immersed into liquid nitrogen for snap freezing.

6.6 Premature Discontinuation of Investigational Agent

Study treatment will be discontinued for any participant who experiences any of the following:

- Pregnancy
- Any Grade 4 or higher infection
- For AEs associated with laboratory evaluations, any of the following lab abnormalities that persist longer than 5 days:
 - i. eGFR < 30 ml/minute/1.73m²
 - ii. WBC ≤ 1.5 x 10⁹/L
 - iii. Platelet count < 50 x 10⁹/L
 - iv. Hemoglobin < 8 g/dL
 - v. ANC < 1.0 x 10⁹/L
 - vi. ALT or AST elevation > 5 times ULN
 - vii. Total bilirubin > 3 times ULN. If Gilbert's disease, total bilirubin > 3 times baseline value.
- For AEs associated with clinical evaluations, any Grade 3 or higher event as defined by the National Cancer Institute-Common Terminology Criteria for Adverse Events (NCI-CTCAE) that is possibly, or definitely related to elotuzumab including anaphylaxis (see **Appendix 7: Clinical Criteria for Diagnosing Anaphylaxis**)[39] or infusion reaction
- Malignancy excluding squamous cell and basal cell carcinoma of the skin
- Disease flare, as defined in Section 3.5.3
- Participants who decide to discontinue the treatment
- The investigator believes that the study treatment is no longer in the best interest of the participant.

Participants will be expected to remain in the study for follow up despite discontinuation of study drug. Participants who discontinue protocol-specified treatment requirements will be treated as medically indicated according to physician discretion.

7 Concomitant Medications

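### Section 6.4.2 lets sites restart study drug after any resolved Grade 3 infection, although Section 6.6 requires permanent discontinuation when that infection is judged related to elotuzumab

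*Combined protocol and SAP*

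**What the plan says.** **Section 6.6** is a list of events for which study treatment is to be stopped. Two items matter here. One is specific to infection and carries no attribution condition: "Any Grade 4 or higher infection". The other is general: "For AEs associated with clinical evaluations, any Grade 3 or higher event as defined by the National Cancer Institute-Common Terminology Criteria for Adverse Events", limited to an event "that is possibly, or definitely related to elotuzumab including anaphylaxis". It makes no exception for infections.

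**Section 6.4.2** sets its permanent stop one grade higher: "Discontinue study drug permanently in the event of a Grade 4 infection". For Grade 3 it takes a different course: "Guidance for proceeding with study drug administration following a Grade 3 infection and resolution includes" four conditions (at least a month since onset, full recovery, treatment completed, judged fit). None concerns relatedness. It adds: "Once the infection resolves, elotuzumab/placebo may be restarted at the next scheduled dose". Its separate COVID-19 text also allows resumption after one month and recovery, again without a relatedness condition.

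**Section 6.1.4.2.2** is the only place that orders the two: "If an infusion is missed for reasons other than those requiring premature discontinuation (Section 6.6), a single intermediate delayed infusion may be permitted". It then tells the reader that "criteria for the resolution of specific adverse events before restarting infusions are given in Section 6.4".

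Section 6.4.2 does not cite Section 6.6, and Section 6.6 does not cite Section 6.4.2.

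**The concern.** A Grade 3 infection judged possibly or definitely related to elotuzumab satisfies both texts: one allows restart, the other requires a stop. Section 6.4.2 is the infection section, so a site managing an infection would naturally turn to it, and nothing there points to the stopping rule.

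The overlap is unlikely to be rare. Section 12.3.2 codes adverse events that could be due to either study product or glucocorticoid as related or possibly related to elotuzumab. Infection is a listed risk of both (Sections 5.1.3 and 5.2.1).

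Three things depend on which text a site follows: whether a participant is re-dosed after a related severe infection, how many discontinuations count toward the Section 11.5 trigger (which refers to Section 6.6), and who stays in the per-protocol set, which requires at least 5 of 6 infusions unless treatment stopped for flare (Section 13.4.1).

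**Working it through.** **Step 1. Compare the rules by case.**

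| Infection | Section 6.4.2 | Section 6.6 | Conflict? |
|---|---|---|---|
| Grade 3, not related | restart allowed | not listed | no |
| Grade 3, possibly or definitely related | restart allowed | must stop | yes |
| Grade 4 or higher, any attribution | must stop | must stop | no |

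Infection falls under the general item of Section 6.6 because the note in Section 12.5.2 counts diagnoses among clinical events.

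**Step 2. How many participants.** The plan gives no figure to reproduce.

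Assumptions, none from the documents: Grade 3 infection risk of 5 to 15% over 48 weeks, averaged over both arms; 50 to 100% of these judged related; uniform onset. All 63 Part 2 participants count, because attribution is blinded. Only onset before the Week 40 infusion matters, since neither rule changes dosing after the last scheduled infusion.

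- Risk r of a related Grade 3 infection over 48 weeks: 0.05 × 0.5 = 0.025 at the low end; 0.15 × 1.0 = 0.15 at the high end. Between them: 0.05 × 1.0 = 0.05 and 0.15 × 0.5 = 0.075.
- Probability before Week 40: p = r × 40/48. Expected participants: 63 × p.
- Expected before Week 32: 63 × r × 32/48, giving 63 × 0.025 × 0.667 = 1.05 up to 63 × 0.15 × 0.667 = 6.30.

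Infusions fall at Weeks 0, 8, 16, 24, 32 and 40. A stop before Week 32 therefore leaves at most four, and the participant leaves the per-protocol set. Under Section 6.4.2, prompt recovery can preserve five.

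Actual re-dosing would differ over a slightly shorter window because of the one-month wait. Its end depends on the last permitted infusion, which Section 6.4.2 puts at Week 40 and Section 6.1.4.2.2 at Week 44. With the Week 40 limit, onset up to about Week 36 matters: 63 × r × 36/48 = 1.2 to 7.1.

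**Step 3. Effect on the Section 11.5 trigger.** It is met by two or more of the first 6 treated in a cohort, and afterwards by more than 20%. I counted only these infections, handled under Section 6.6, with n the number of Cohort 2 participants so far, taken in order of entry with full follow-up.

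- First 6: P(X ≥ 2), X ~ Binomial(6, p).
- Afterwards: the probability that the cumulative count exceeds 0.2n at some n from 7 to 63. The threshold is floor(0.2n) + 1: 2 at n = 7, 3 at n = 10, 5 at n = 20, 13 at n = 63. Two among the first 6 already exceed 20% at n = 7 (2/7 = 28.6%), so this probability covers both parts.
- Final look only: P(X ≥ 13), X ~ Binomial(63, p), shown for contrast.

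| r | p | Expected of 63 | 2+ of first 6 | >20% at some n, 7–63 | 13+ of 63 (final look only) |
|---|---|---|---|---|---|
| 0.025 | 0.0208 | 1.31 | 0.006 | 0.015 | <0.000001 |
| 0.05 | 0.0417 | 2.62 | 0.023 | 0.058 | 0.000002 |
| 0.075 | 0.0625 | 3.94 | 0.049 | 0.125 | 0.00012 |
| 0.15 | 0.125 | 7.88 | 0.167 | 0.44 | 0.046 |

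These lean high because participants already off drug are not removed. As an illustration, suppose 39% stop for flare by Week 48 at a uniform rate (the prednisone-alone relapse figure in Section 1.1.2, applied to everyone as an assumption). The factor 40/48 = 0.833 becomes (40 − 0.39 × 40²/96)/48 = 0.698. Expected participants become 63 × 0.025 × 0.698 = 1.1 to 63 × 0.15 × 0.698 = 6.6.

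**The case against.** The strongest reply is that the two sections can both be obeyed. Section 6.6 is mandatory and Section 6.4.2 is permissive, so a site that stops drug under 6.6 breaches nothing in 6.4.2. The restart guidance then applies to whatever 6.6 leaves, namely unrelated Grade 3 infections. Section 6.1.4.2.2 screens out Section 6.6 cases before sending the reader to Section 6.4, and Section 11.5 defines permanent discontinuation by reference to 6.6. This argument stands as to which rule prevails. It does not remove the gap: the screen in 6.1.4.2.2 covers only a delayed make-up infusion, while 6.4.2 separately allows resumption at the next scheduled dose and says nothing of 6.6.

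Four stronger readings are tempting, and the documents do not support them.

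- *The text is evenly balanced.* A reader might take the Grade 4 infection item in 6.6 to be its only infection rule. That item has its own purpose: it stops drug for unrelated Grade 4 infections, which the related-event item would miss.
- *COVID-19 restart has no grade limit.* The Grade 4 stop in the same section applies to it. Only relatedness is unaddressed.
- *The trigger could halt the trial.* It starts a DSMB review. For this event Section 12.11.3 lets the study proceed, pausing consent and enrolment only if the DSMB has not met within two weeks.
- *Thirteen of 63 gives the trigger probability.* It is only the final look. Section 11.5 does not confine the 20% rule to full enrolment.

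**Conclusion.** The concern holds as a minor one. For a related Grade 3 infection the protocol requires a stop in one section and permits restart in another. Section 6.6 is the better-supported rule, but Section 6.4.2 as written can lead a site to re-dose a participant who must be discontinued.

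The size rests on assumed infection and attribution rates: about 1 to 8 of 63 participants under both rules before Week 40, about 1 to 6 of them before Week 32, and a probability of about 0.015 to 0.44 that these infections alone exceed 20% at some point. The upper end needs 15% risk with every infection judged related.

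The harm is limited. The restart conditions and the investigator's freedom to stop drug offer some protection, Grade 3 infections are reported within 24 hours under either rule, and the DSMB reviews safety twice a year. The per-protocol analysis is supportive. The primary mITT analysis is not directly affected.

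**What to change.** In Section 6.4.2, limit the Grade 3 restart guidance, and the COVID-19 restart text when the infection is Grade 3, to infections judged not related to elotuzumab. Add that possibly or definitely related Grade 3 infections are handled under Section 6.6, with permanent discontinuation. If the sponsor in fact intends to allow resumption after related Grade 3 infections, the exemption has to be written into the clinical-event item of Section 6.6 instead, leaving its Grade 4 infection item in place.

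The cost is one sentence or cross-reference. Data collection, sample size and the primary analysis do not change.
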